### **12.3 Randomisation**

Patients who meet all criteria for enrolment will be randomised to double-blind treatment in a 1:1 ratio either to safinamide or placebo at visit 2 (day 1) and will be allocated a medication kit number according to the randomised treatment group. The randomisation will be done with blocks sized of unequal length to guarantee a good balance between safinamide and placebo at any stage of the enrolment minimizing the procedure selection bias.

#### **Patient identification:**

Each patient who has signed an informed consent form and is screened will be allocated to a 3-digit screening number comprising the prefix 'xx' where xx is the unique site number and a 3-digit number representing the sequential order in which they are screened, e.g. 01-001, 01-002, 02-001 etc.

The number will be assigned by the eCRF/IWRS upon entry in the system.

#### **Kit number**

At randomisation, the eCRF/IWRS will allocate a unique medication kit number.

### **12.4 Investigational Medicinal Product Accountability**

IMP inventory and accountability records will be kept by the Investigator or Pharmacy. The following rules are to be followed:

- a) the Investigator will keep IMP in a pharmacy, or a locked and secure storage facility, accessible only to those individuals authorised by the Investigator to dispense the IMP.
- b) the inventory will be maintained by the Investigator or pharmacist or other nominated individual. The inventory will be done by means of a specific "Subject/Study Investigational Product Accountability Record & Investigational Product Reconciliation Log" provided by the CRO/IWRS and will include details of IMP received and a clear record of when they were dispensed and to which patient. The log shall indicate the

quantity and description of all IMPs on hand at any time during the course of the clinical trial.

- c) at the conclusion or termination of the clinical trial, the Investigator agrees to conduct a final IMP inventory and to record the results of the inventory on an appropriate form provided by the CRO/IWRS (Investigational Product Return Form). The monitor will check that IMP accountability was correctly performed. According to instructions, the Investigator will return all original IMP containers, whether empty or containing test preparations, to local depot delegated by the CRO for final reconciliation and destruction. Sites can also handle destruction.
- d) the IMP can be dispensed to patients only by Investigator/pharmacist who agrees not to supply IMP to any person except those named as Investigators/Co-Investigators as detailed in the Site Signature/Delegation Log, and to patients in this trial.

## **12.5 Treatment of Overdose**

Reports of overdose with safinamide have been rare. The anticipated pattern of events or symptoms following intentional or accidental overdose with safinamide is that related to its pharmacodynamic profile (MAO-B inhibition with activity-dependent inhibition of sodium channels). The symptoms of excessive MAO-B inhibition (increase in dopamine level) could include hypertension, postural hypotension, hallucinations, agitation, nausea, vomiting and dyskinesia.

There is no known antidote to safinamide or any specific treatment for a safinamide overdose. If a significant overdose should occur, safinamide treatment should be discontinued and supportive treatment should be administered as clinically indicated.

## **13.0 CLINICAL TRIAL AMENDMENTS**

Changes to the Clinical Trial Protocol (CTP) can be made by preparing written amendments to be agreed and signed by the Investigator and Sponsor. A substantial amendment may not be implemented without a favourable opinion of the Ethics Committee (EC) and Competent Authority (CA), unless the changes consist of urgent safety measures to protect trial patients.

Amendments which are non-substantial amendments as defined by present regulations can be sent to EC/CA for notification and may be implemented at the site before EC/CA notification according to local rules.

## **14.0 DEVIATIONS FROM THE CLINICAL TRIAL PROTOCOL**

Any major or critical deviation which may have an impact on study results and safety of the patients should be immediately reported to Sponsor/CRO and notified to Regulatory Authorities (EC/CA) according to local regulations. A decision will be taken together with the Sponsor whether or not the patient affected by the deviation from the CTP is to continue in the study. The eCRF will describe the deviation from the CTP. A deviation log will be maintained to track actual deviations and decisions taken, including all deviations occurred.

In case of an emergency deviation from the CTP applicable only when an emergency situation has to be faced for a patient, this deviation will be only applied to that individual.

In such an emergency the Investigator must contact the CRO by telephone as soon as possible.

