### **15.0 CLINICAL TRIAL WITHDRAWALS/ DROP-OUTS**

Patients may be withdrawn from the study at their own request or at the discretion of the Investigator for one of the following reasons:

- Patient withdraws consent to participate.
- 
- Pregnant female patients must be withdrawn from the study without delay. Follow-up should be performed in accordance with [Section 17.10](#).
- Patient has an AE that, in the opinion of the Investigator, requires the patient's discontinuation. Follow-up should be in accordance with [Section 17.9](#).
- Any clinically significant abnormal findings in physical examination, ECG, vital signs, haematology, chemical chemistry which, in the opinion of the Investigator may compromise the safety of the patient in the study or interfere with evaluation of the IMP or reduce the patient's ability to participate in the study.
- Intercurrent illness requiring pharmacological treatment with a non-permitted drug or a drug which interacts in any way with the test treatment or with study evaluations.
- Patient is non-compliant with the protocol.

- Continuation in the study would be detrimental to the patient's safety in the opinion of the Investigator.
- The Investigator or the Sponsor, for any reason, stops the study.
- Sponsor, CA, or EC terminate the trial at an individual site.

Patients who prematurely withdraw from the study while receiving study medication should complete the EOT Visit assessments, when possible. Patients must return the medications and details regarding AEs and concomitant medications will be collected.

Patients who are withdrawn from the study will not be replaced. In the event that a patient discontinues from the study prematurely due to an AE or SAE, they will be followed until the event has resolved (returns to normal or baseline values) or has stabilised.

The reason for withdrawal of a patient from the study or premature discontinuation of the treatment must be fully documented in the eCRF as well in source documents. Follow-up for withdrawn patients follows the procedures described in [Section 17.8](#) and [Section 17.9](#).

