## 10.2 Compliance

The prescribed dosage, timing and mode of administration of study medication may not be changed. Study medication accountability and patient compliance will be documented throughout the treatment period using study-specific study medication dispensing and return record forms.

The evaluation of compliance will be done using the following formula:

$$\% \text{ of administered drug} = 100 \times \frac{\text{Total number of administered doses}}{\text{Total number of scheduled doses}^*}$$

*\*1 dose x number of days between visits*

Patients will be asked to return all unused medication. From visits 3 to 6 (weeks 2 to 16), the study medication dispensed at the previous visit will be retrieved by the Investigator and compliance assessed by tablet count.

Non-compliance is defined as taking less than 80% or more than 120% of study medication during any visit-to-visit evaluation period.

Patients exhibiting non-compliance as assessed by tablet counts should be counselled on the importance of good compliance to the study dosing regimen.

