## 15.0 CLINICAL TRIAL WITHDRAWALS/ DROP-OUTS

Patients may be withdrawn from the study at their own request or at the discretion of the Investigator for one of the following reasons:

- Patient withdraws consent to participate.
- Pregnant female patients must be withdrawn from the study without delay. Follow-up should be performed in accordance with [Section 17.10](#).
- Patient has an AE that, in the opinion of the Investigator, requires the patient's discontinuation. Follow-up should be in accordance with [Section 17.9](#).
- Any clinically significant abnormal findings in physical examination, ECG, vital signs, haematology, chemical chemistry which, in the opinion of the Investigator may compromise the safety of the patient in the study or interfere with evaluation of the IMP or reduce the patient's ability to participate in the study.
- Intercurrent illness requiring pharmacological treatment with a non-permitted drug or a drug which interacts in any way with the test treatment or with study evaluations.
- Patient is non-compliant with the protocol.
- Continuation in the study would be detrimental to the patient's safety in the opinion of the Investigator.
- The Investigator or the Sponsor, for any reason, stops the study.
- Sponsor, CA, or EC terminate the trial at an individual site.

Patients who prematurely withdraw from the study while receiving study medication should complete the EOT Visit assessments, when possible. Patients must return the medications and details regarding AEs and concomitant medications will be collected.

Patients who are withdrawn from the study will not be replaced. In the event that a patient discontinues from the study prematurely due to an AE or SAE, they will be followed until the event has resolved (returns to normal or baseline values) or has stabilised.

The reason for withdrawal of a patient from the study or premature discontinuation of the treatment must be fully documented in the eCRF as well in source documents. Follow-up for withdrawn patients follows the procedures described in [Section 17.8](#) and [Section 17.9](#).

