## **20.4 Statistical Analyses**

### **20.4.1 General Statistical Considerations**

All data captured on eCRFs will be available as listings.

The statistical analysis will be performed by the CRO. If not otherwise stated all statistical analyses and data tabulations will be produced using SAS® for Windows release 9.4 (64-bit) or later (SAS Institute Inc., Cary, NC, USA).

Unless stated otherwise, all available data from withdrawn subjects will be included in the analysis up to the time of withdrawal.

The primary study objective will be assessed by testing the superiority of Safinamide compared to placebo and will be achieved if the analysis on primary end-point will be found statistically significant. The key secondary objective will be always assessed through a superiority analysis of Safinamide compared to placebo and, similarly, will be reached if the analysis on key secondary end-point will be found statistically significant. Conversely, the analyses on the remaining secondary efficacy endpoints will be treated as non-key secondary objectives since they will be performed only to support primary endpoints findings.

All tests will be two-sided and performed at the significance nominal level of  $\alpha = 0.05$ . Details are reported in Section 20.4.5.

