##### Full Analysis Set

The Full Analysis Set (FAS) will comprise all patients who provided informed consent, were randomized and received at least 1 dose or partial dose of the IMP.

Primary analyses will be performed on the FAS population with exclusions from the randomized defined and justified in the SAP.

Following the randomized principle, patients will be analyzed according to the treatment they have been assigned to at the randomization.

The FAS will be used to produce summaries of baseline patient characteristics and for the analysis of all efficacy endpoints.

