#### **20.4.3 Efficacy Data**

The FAS population will be used for the primary analyses of each of the efficacy endpoints whilst results from supplemental analyses using the Per Protocol Population will be compared to those based on the FAS population to assess the effects of dropouts, missing data, protocol violations and deviations.

The distributions of all the efficacy endpoints listed in Section 20.2 will be summarized by treatment group and time point. Counts and percentages will be reported with the latest computed based on the numbers of patients with non-missing observations. The percentages will be suppressed when the count is zero in order to draw attention to the non-zero counts. Furthermore, efficacy endpoints will be further summarized by arithmetic means, standard deviations, medians quartiles, minima and maxima.

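### Sections 14.0 and 15.0 allow withdrawal from the study for a deviation or non-compliance, which creates avoidable missing week-16 data and weakens the FAS-versus-PP comparison

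*Protocol*

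**What the plan says.** The relevant sentences are the same in protocol version 1.0 and in the amended version 2.0.

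- **Section 14.0.** For a major or critical deviation that may affect study results and patient safety, it is decided jointly with the sponsor "whether or not the patient affected by the deviation from the CTP is to continue in the study".
- **Section 15.0.** The reasons for which a patient may be withdrawn from the study include "Patient is non-compliant with the protocol". Adverse events, abnormal clinical findings and continuation harmful to the patient have their own bullets, and so does withdrawal of consent.
- **Section 15.0, after withdrawal.** "Patients who prematurely withdraw from the study while receiving study medication should complete the EOT Visit assessments, when possible". No further efficacy visits to week 16 are planned.
- **Section 10.2.** Patients found non-compliant by tablet count "should be counselled on the importance of good compliance to the study dosing regimen".
- **Section 20.4.2.** The FAS takes all consenting patients who "were randomized and received at least 1 dose or partial dose of the IMP", analysed as randomised. Patients with major deviations are excluded from the PP set by a documented decision before unblinding.
- **Section 20.4.1.** "all available data from withdrawn subjects will be included in the analysis up to the time of withdrawal".
- **Section 20.4.4.** Missing primary and key secondary values are multiply imputed, with last observation carried forward (LOCF) as the sensitivity analysis. The imputation model is left to the SAP.
- **Section 20.4.3.** PP results "will be compared to those based on the FAS population to assess the effects of dropouts, missing data, protocol violations and deviations".

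**The concern.** The analysis sections deal with deviators in the usual way: keep them in the FAS as randomised, exclude them from the PP set, and compare the two. Sections 14.0 and 15.0 add a second route, in which the patient leaves the study and the week-16 outcome is never observed. Since safety and consent have their own bullets in Section 15.0, what the non-compliance bullet adds is removals that need neither.

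Two things are at stake. First, outcomes that could have been measured become missing at someone's discretion. Under Section 10.1.6 the investigator goes through the diary with the patient at each visit, so the person exercising that discretion has seen the outcome data. Even under blinding, removal may therefore be related to response. Second, each removed deviator enters the FAS with an imputed week-16 value. If that value is modelled on adherent patients, the FAS estimate moves towards the PP estimate, and agreement between the two says less about the influence of deviations. No SAP can recover data that sites were allowed not to collect.

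**Working it through.** **The plan's own figures.** Inputs from Section 20.3: difference 0.9 h, SDs 2.35 and 2.06, 130 evaluable per arm, two-sided alpha 0.05, 15% attrition.

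- SE = √[(2.35² + 2.06²)/130] = √(9.7661/130) = 0.274 h.
- Power ≈ Φ(0.9/0.274 − 1.96) = Φ(1.32) = 90.7%; the noncentral t gives 90.5%. The stated 90% is reproduced.
- 260/(1 − 0.15) = 305.9, so 306. This is also reproduced.

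No stated number is wrong on this point.

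**What happens to a removed deviator.** The patient has been randomised and dosed, so is in the FAS. Data count up to withdrawal. An early-termination diary and pain score may exist. The week-16 value is imputed in the primary analysis and carried forward in the sensitivity analysis. What is lost is the observed week-16 outcome, not membership of the FAS.

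**Illustration of size.** The following are assumptions, not figures from the protocol: a share v of each arm deviates (5% or 10%, within the planned 15% attrition); the effect is 0.9 h in adherent patients and e in deviators (0 or 0.45 h); imputation borrows from adherent patients in the same arm.

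- Deviators followed: FAS effect = 0.9(1 − v) + e·v.
- All deviators removed and imputed: FAS effect ≈ 0.9, the same as PP.

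| v | e (h) | Followed (h) | Removed and imputed (h) | Shift (h) |
|---|---|---|---|---|
| 5% | 0 | 0.855 | 0.90 | 0.045 |
| 5% | 0.45 | 0.878 | 0.90 | 0.023 |
| 10% | 0 | 0.810 | 0.90 | 0.090 |
| 10% | 0.45 | 0.855 | 0.90 | 0.045 |

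A simulation with 153 per arm and 4,000 trials per setting checked the rows with e = 0. Removed patients were filled in by within-arm regression on an earlier visit, assuming an earlier-visit effect of 0.7 h and correlation 0.6. At v = 5% it gave 0.854 followed, 0.899 imputed and 0.898 PP. At v = 10% it gave 0.811, 0.900 and 0.899.

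**LOCF.** With the same assumed earlier effect of 0.7 h, LOCF gives 0.9(1 − v) + 0.7v = 0.89 h at 5% and 0.88 h at 10% (simulated 0.889 and 0.882). It does not coincide with PP.

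**Partial removal.** If only a fraction r of deviators is removed, the remaining FAS–PP gap is (0.9 − e)·v·(1 − r). For v = 10%, e = 0 and r = 0.5 it is 0.9 × 0.10 × 0.5 = 0.045 h, half of 0.090 h. The gap disappears only at r = 1.

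**Precision.** Following 5–10% of 153 per arm adds about 8 to 15 observed patients, so 130 becomes about 138 to 145. The SE then falls from 0.274 to √(9.7661/138) = 0.266 or √(9.7661/145) = 0.260 h.

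**The case against.** A reader might infer that the FAS drops these patients and that the FAS-versus-PP comparison therefore shows nothing. The protocol supports neither. FAS membership depends only on consent, randomisation and one full or partial dose. Withdrawal is also optional in both sections: non-compliance by tablet count leads to counselling, and prohibited medication is recorded as a deviation. Deviators who continue, or who are identified only at the review before unblinding, keep observed week-16 data in the FAS and leave the PP set. The LOCF analysis gives a further contrast.

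Other objections also have force.

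- The trigger in Section 14.0 mentions patient safety as well as study results, so that section cannot be read as ignoring safety. Only the non-compliance bullet in Section 15.0 carries no such condition.
- The early-termination visit may capture the patient's state after the deviation. It is not a week-16 value, and how it enters the imputation is for the SAP.
- Counselling in Section 10.2 and optional withdrawal in Section 15.0 can be successive steps. They are not a contradiction, although no rule says when one gives way to the other.
- The direction is not certain. A non-permitted drug could shift outcomes in either arm.

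The core stands: discretionary removal without a safety or consent ground is allowed, week-16 efficacy data then stop being collected, and the PP set already exists to deal with deviators.

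**Conclusion.** The concern holds in a limited form. Sections 14.0 and 15.0 permit avoidable, possibly informative loss of week-16 diary and pain data. This weakens the comparison in Section 20.4.3 without emptying it, and fits poorly with the handling of deviators in Section 20.4.2.

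Under the assumptions above, the FAS effect would be about 0.90 h instead of 0.81–0.88 h. That shift of 0.02–0.09 h is at most about a third of the 0.274 h standard error (0.09/0.274 = 0.33). It rests on an assumed share of deviators, an assumed residual effect, removal of all of them, and imputation from adherent patients in the same arm. With partial removal it is smaller, and with other kinds of deviation it could run the other way. The planned power and the 306 randomised are not affected. The case for a change rests less on the size of this shift than on the fact that the loss is avoidable and cannot be repaired at the analysis stage.

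**What to change.** In Sections 14.0 and 15.0, separate stopping study drug from leaving the study. Section 15.0 already names both events in its documentation sentence but gives one list of reasons for them.

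State that a deviation or non-compliance alone, including use of a non-permitted drug, does not end data collection. The patient attends the scheduled visits with diary and pain score to week 16 unless consent is withdrawn or the investigator judges that staying would be unsafe. The deviation is recorded and handled through the PP set.

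Decisions on study drug and sponsor review of safety-relevant deviations stay under the existing rules. The remaining Section 15.0 bullets must be reconciled with the new sentence, in particular those on illness needing a non-permitted drug and on findings that may interfere with evaluation of the study drug.

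The cost is a short amendment and some further visits already in the flow chart. Under the assumed 5–10%, these would concern about 15 to 31 of 306 patients (0.05 × 306 = 15.3; 0.10 × 306 = 30.6). The FAS estimate may come out slightly less favourable. The sample size does not change.

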#### **14.1 Code Breaking**

The code for any individual patient will not be broken by the Investigator during course of the trial except in the circumstance of an SAE of life-threatening significance.

In case of emergency, unblinding of the treatment code will be done through IWRS. The treatment group will be disclosed and confirmation will follow (by fax and/or notification email). The IWRS will be designed to send a confirmation (by fax and/or notification email) to the site for every transaction performed by the site users. Site users will be provided with usernames and passwords to access the IWRS.

Unblinding of the study treatment must be done in case of an emergency situation, where the Investigator considers it essential to know what treatment the patient was taking. Access to the unblinding option will be granted only to the Investigators and sub-Investigators at the sites. If the treatment code has been opened, this must be recorded in the eCRF.

**The IWRS will immediately notify the Sponsor/CRO pharmacovigilance and the Clinical Trial Monitor whenever a treatment code is unblinded.**

Users from CRO and Sponsor Pharmacovigilance will have their own passwords to unblind patients in case of suspected unexpected serious adverse reactions (SUSARs) to be reported to the CA and ECs as applicable.

### **15.0 CLINICAL TRIAL WITHDRAWALS/ DROP-OUTS**

Patients may be withdrawn from the study at their own request or at the discretion of the Investigator for one of the following reasons:

- Patient withdraws consent to participate.
- 
- Pregnant female patients must be withdrawn from the study without delay. Follow-up should be performed in accordance with [Section 17.10](#).
- Patient has an AE that, in the opinion of the Investigator, requires the patient's discontinuation. Follow-up should be in accordance with [Section 17.9](#).
- Any clinically significant abnormal findings in physical examination, ECG, vital signs, haematology, chemical chemistry which, in the opinion of the Investigator may compromise the safety of the patient in the study or interfere with evaluation of the IMP or reduce the patient's ability to participate in the study.
- Intercurrent illness requiring pharmacological treatment with a non-permitted drug or a drug which interacts in any way with the test treatment or with study evaluations.
- Patient is non-compliant with the protocol.

- Continuation in the study would be detrimental to the patient's safety in the opinion of the Investigator.
- The Investigator or the Sponsor, for any reason, stops the study.
- Sponsor, CA, or EC terminate the trial at an individual site.

Patients who prematurely withdraw from the study while receiving study medication should complete the EOT Visit assessments, when possible. Patients must return the medications and details regarding AEs and concomitant medications will be collected.

Patients who are withdrawn from the study will not be replaced. In the event that a patient discontinues from the study prematurely due to an AE or SAE, they will be followed until the event has resolved (returns to normal or baseline values) or has stabilised.

The reason for withdrawal of a patient from the study or premature discontinuation of the treatment must be fully documented in the eCRF as well in source documents. Follow-up for withdrawn patients follows the procedures described in [Section 17.8](#) and [Section 17.9](#).

